15.5	Site Initiation	49
15.6	Monitoring	50
15.7	Required Reports	50
16	STUDY REQUIREMENTS	52
16.1	Quality Assurance	52
16.2	Monitoring	53
17	PROCEDURES AND INSTRUCTIONS	55
17.1	Special safety-related procedures	55
17.2	Administrative procedures	55
17.3	Ethics and Good Clinical Practice	55
APPEND	DIX A - STUDY SCHEDULE	56
APPEND	DIX B- Supplemental TRANSPLANTATION /OTHER APPENDICES	58
APPEND	DIX C – Supplemental TRANSPLANTATION	59
REFEREI	NCE LIST	60

CONFIDENTIAL	Clinical Protocol	DATE	Р	age
		9Dec2019		T
	mented Disc Regeneration in the Treatment of the or without Intervertebral Disc Herniation –	WRITER TG, DB, PW	NO. 9	REV 6

STUDY CONTACTS

Sponsor: Vivex Biologics, Inc.

[name]

[contact]

Medical Monitor: H. [name]

Chief Medical Officer Vivex Biologics, Inc.

[contact]

Clinical Representative: [name]

Clinical Program Manager

Vivex Biologics, Inc.

[contact]

Principal Investigator: [name]

[name]

[name]

[name] [contact]

CONFIDENTIAL	Clinical Protocol	DATE 9Dec2019	P	age
	mented Disc Regeneration in the T reatment of the or without Intervertebral Disc Herniation –	WRITER TG, DB, PW	NO. 10	REV 6

PROTOCOL SYNOPSIS

Title	Viable Allograft Supplemented Disc Regeneration in the Treatment of Patients with Low Back Pain with or without Intervertebral Disc Herniation – VAST Trial
Objective	To evaluate the safety and efficacy of viable allograft transplantation for the treatment of patients with symptomatic disc degeneration and tissue loss
Study Design	Multi-center, prospective, parallel, triple arm study to assess patients who participated in the VAST trial and receiving either viable allograft, saline, or allograft after cross-over. These patients will be evaluated at baseline, injection, 6 months, and 12 months. Subjects will then have an option for a 24 months and 36 months extension after their index procedures. Patients who received saline or active allograft in the VAST study, will be allowed to receive viable allograft and followed for an additional 12 and 24 months after that election. These subjects will need to meet initial inclusion/exclusion criteria again before another injection.
Endpoints	 Primary: Improvement in Oswestry Disability Index (ODI) at 6 and 12 months after treatment. Durability of Oswestry Disability Index (ODI) at 24 and 36 months after initial inclusion compared with 12 month improvement. Improvement in Visual Analogue Scale of Pain Intensity (VASPI) at 6, and 12 months after treatment. Durability of Improvement in Visual Analogue Scale of Pain Intensity (VASPI) 24 months and and 36 months after initial inclusion compared with 12 month improvement.
	Secondary Page 10 of 62

CONFIDENTIAL	Clinical Protocol	DATE	P	age
		9Dec2019		
	mented Disc Regeneration in the $\underline{\mathbf{T}}$ reatment of th or without Intervertebral Disc Herniation –	WRITER TG, DB, PW	NO. 11	REV 6

	 Improvement in ODI, SF-36, and VASPI at 6 and 12 months after treatment Improvement in ODI, SF-36, and VASPI scores for optional 24 month and 36 month follow up subjects X-ray and MRI measurements at 6 and 12 months after treatment AE/SAE rates after treatment Hospitalization rate at 12, 24, or 36 months after treatment Re-operation rate at 12, 24, or 36 months after treatment Resource utilization following treatment and at 6 and 12 months (and optional 24 & 36 month) follow up visits 		
Study Population	Patients evaluated for degenerative intervertebral disc disease demonstrating Pfirrmann Grade [3-6] by MRI		
Clinical Sites	Up to twenty (20) sites in the United States		
Sample size and	Approximately 220 subjects randomized to viable allograft or placebo or control in 3.5:1:1 ratio:		
randomization	$n_{active} = 140$ $n_{placebo} = 40$ $n_{control} = 40$		
	For study extension: The original randomized population will be pooled and reconsented for an optional follow up for 24 and 36 months.		
Study Design	The study is composed of three separate phases. There will be the Screening Phase followed by the Active Phase equaling 12 months then followed by the optional long term follow up at 24 months and 36 months. Patients need to meet entry criteria for all phases.		

CONFIDENTIAL	Clinical Protocol	DATE 9Dec2019	Р	age
	mented Disc Regeneration in the T reatment of the or without Intervertebral Disc Herniation –	WRITER TG, DB, PW	NO. 12	REV 6

During the Screening Phase, subjects will be assessed for study eligibility, X-ray and MRI within the previous 6 months, SF-36, ODI, and VASPI to establish a baseline for participation. If meeting eligibility, they will be scheduled for allograft treatment, placebo (saline) treatment, or conservative care treatment. Those who meet the Active Phase entry criteria will be randomized at Day 0 to either receive the viable allograft, placebo as saline, or be assigned to continue conservative treatment. Specified subjects, as noted below, will return to the clinic for a safety assessment 1 month after the transplant, and subsequently at 6, and 12 months for safety and efficacy assessments. Patients who continue conservative care will be evaluated at 3 months, as well as 6 and 12 months. Physicians at their discretion can bring subjects back for follow-up to assure safety at any time point throughout the duration of the study. The first 24 patients to be randomized (at least 4 from each treatment group) will have an additional study visit 1 month after treatment. All data from the 1-month study visit will be collected and reviewed by the Steering Committee to confirm that enrollment can continue. Subjects will have the option to continue with a long-term follow up at time points of 24 and 36 months. Questionnaires will be completed over the phone with the study coordinator's prompting or during an in-office visit. All randomized subjects will also have the option to receive an allograft injection during the 24 month office visit after meeting inclusion/exclusion criteria. Able to provide an English written Informed Consent **Inclusion Criteria** • Age 18 to 60 years inclusive • Male or female Body mass index <35 Pfirrmann Grade [3-6]

CONFIDENTIAL	Clinical Protocol	DATE 9Dec2019	P	age
	mented Disc Regeneration in the $\underline{\mathbf{T}}$ reatment of th or without Intervertebral Disc Herniation –	WRITER TG, DB, PW	NO. 13	REV 6

 Radiographic confirmation by MRI/X-ray of: (1) translational instability defined as ≤5 mm, or (2) angular instability defined as ≤5° Back pain (with or without radicular leg pain) measured by: (1) ODI of at least 40%, and (2) VASPI of at least 40mm Pathologic level between L1 and S1 1 or 2 vertebral level involvement that has been evaluated for at least 6 months and treated with conservative care Symptomatic back pain attributable to intervertebral disc for a minimum of 6 months No previous surgical treatment at the disc level(s) being considered Psychosocially, mentally and physically able to fully comply with this protocol, and follow-up schedule Ability to undergo allograft transplantation Life expectancy >2 years No contraindications to MRI No history of malignancy (basal cell carcinoma) or chronic infectious disease (e.g. HIV, Hepatitis) Agree to use appropriate contraception; not planning on becoming pregnant for 24 months after treatment Patient disc for transplant confirmed by inter-discal pressure measurement, or disc-imaging study. No signs or symptoms of infection No chronic use (>7 consecutive days) of anticoagulants (such as aspirin) or NSAIDs prior to treatment
 Seropositive or seronegative spondyloarthropathy Type III Modic changes Prior surgeries of segments between L1 and S1 Chemonucleolysis or percutaneous laserectomy of the affected disc prior to the study Chronic facet syndrome

CONFIDENTIAL	Clinical Protocol	DATE 9Dec2019	P	age
	mented Disc Regeneration in the $\underline{\mathbf{T}}$ reatment of th or without Intervertebral Disc Herniation –	WRITER TG, DB, PW	NO. 14	REV 6

	 Stenosis of the spinal canal that is moderate to severe or more in degree Spondylodiscitis Spondylolisthesis (lysis and degenerative) Severe motor deficit or cauda equina disorder based on investigator determination Congenital abnormalities of the spinal nerves Pelvic and inguinal angiopathy Neurogenic inguinal syndrome Syringomyelia Diastenomatomyelia Traumatic neurological disorders Diseases of the kidney (nephritis, pyelonephritis) Other severe diseases of any other major body system as judged by the investigator Regular intake of systemic steroids Malignant diseases of any solid organ or any hematologic malignancy during the previous 5 years Patients who have participated in a clinical trial within the last month prior to inclusion Moderate to severe or greater lumbar stenosis of both transplantation endplates and adjacent levels
Treatment Strategy	Single, or two-level intervertebral disc treatment with viable allograft, placebo, or conservative care treatment for Pfirrmann grade III - VI disc imaging assessment
Statistical Analysis	Primary analysis: The primary efficacy analysis will be performed on the modified intent-to-treat (MITT) population. The MITT population is defined as all subjects who underwent the viable allograft treatment or placebo treatment, and at least one valid post-transplant assessment of ODI and VASPI. The null hypothesis is that there is no difference in ODI at 12 months following viable allograft implantation between the three treatment groups 1.) Allogeneic Cells with supplemental

CONFIDENTIAL	Clinical Protocol	DATE 9Dec2019	P	age
	mented Disc Regeneration in the T reatment of th or without Intervertebral Disc Herniation –	WRITER TG, DB, PW	NO. 15	REV 6

micronized nucleus pulposus, 2.) saline, or 3.) conservative, non-surgical, care.

For all Screening and Active Phase baseline data, descriptive statistics will be presented. A hierarchical test procedure will be applied. In the first step the distributions of the pre-post difference of the groups will be compared using Wilcoxon rank-sum-test. In case of a significant result, a responder analysis will be done using Fisher's exact test. All secondary variables will be analyzed in an exploratory way using adequate statistical procedures

CONFIDENTIAL	Clinical Protocol	DATE	Р	age
		9Dec2019		ı
	mented Disc Regeneration in the Treatment of the or without Intervertebral Disc Herniation –	WRITER TG, DB, PW	NO. 16	REV 6
VAST-001-017	in of without intervertebral bisc hermation –		10	

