3 OBJECTIVE

The objective of this study is to evaluate the safety and efficacy of viable allograft transplantation for the treatment of patients with symptomatic disc degeneration and tissue loss.

The primary criterion is the outcome of the Oswestry Low Back Pain Disability Questionnaire (OPDQ) modified according to Hudson-Cook and calculated as the Oswestry Disability Index (ODI) at 6 and 12 months after transplant, and the Visual Analogue Scale of Pain Intensity (VASPI) at 6, and 12 months following allograft supplementation. Secondary parameters of efficacy will include SF-36. Structural outcomes will be assessed using X-ray and Magnetic Resonance Image (MRI) measurements at 12 months. Safety will be assessed by the incidence and severity of adverse events (AEs) and clinically important changes in laboratory tests. All subjects (excluding conservative care crossover subjects) will be randomized to include MRI at 6-month follow-up (MRI or no MRI, ratio 1:1) in addition to all other assessments. Subjects randomized to conservative care will be assessed at 3 months. If at 3 months these subjects demonstrate a significant decline in condition, they will be offered the option to receive allograft treatment and will be followed for the subsequent 6 and 12 months. The conservative care subjects that crossover to the allograft treatment group will all receive an MRI at 6-month and 12-month follow-up after allograft treatment.

A correlation of the clinical results (scores) and the morphological results (X-ray, MRI) will be evaluated. All additional efficacy and safety data will be analyzed descriptively.

The optional long-term follow up will allow for additional objectives to be analyzed. At 24 and 36 months, subjects will have the opportunity to fill out VASPI, ODI, SF-36, and Resource Utilization forms which will be analyzed and compared to the original 12-month data. The active allograft and placebo cross over to allograft treatment at 24 months will also be asked to fill out the same questionnaires. This data will be compared to the first 12 months of data in the placebo group.

CONFIDENTIAL	Clinical Protocol	DATE 9Dec2019	P	age
	mented Disc Regeneration in the T reatment of th or without Intervertebral Disc Herniation –	WRITER TG, DB, PW	NO. 18	REV 6

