6 STUDY DESIGN

This is a, prospective, randomized, parallel-arm, multicenter study that will enroll up to 220 evaluable patients at up to 20 clinical sites. The outcomes of this trial will be based on assessment of primary and secondary endpoints at 6 and 12 months after treatment of supplementary allograft compared to conservative care in subjects who have pain attributable to disc degeneration as judged by MRI scoring (Pfirrmann), physical examination, and patient reported pain. Optional long term follow up at 24 and 36 months for all randomized subjects will allow for additional secondary endpoints to analyze pain.

The study is composed of three phases – the Screening Phase (enrollment), Active Phase (12 months) and the optional follow up period (additional 24 months). As outlined in Figure 1, there is an indeterminate overlap of up to 14 days between the end of the Screening Phase and the start of the Active Phase for individual subjects in order to evaluate the protocol, and consent to their participation. After completing the Informed Consent procedure, screening and study specific procedures can be performed. Only patients that meet the entry criteria for both phases are eligible and can participate in this study.

During the 14 days of the Screening Phase (Day -14 to Day 0), patients will be assessed for study eligibility to establish their baseline condition, and will be randomized to either conservative care (maintaining current level of care), or be provided with supplementary allograft transplantation (Day 0 of the Screening Phase), or receive placebo treatment (saline). All patients who are randomized to conservative care in the Screening Phase (Day -14 to Day 0), will be evaluated as per standard of care and will be assessed along with those who are selected for eligibility to enter the Active Phase of allograft transplantation.

[figure not shown]
The first 24 subjects randomized (at least 4 subjects from each group) will return to the clinic for a safety assessment 1 month after treatment. Subsequent clinic visits will occur at 6 and 12 months following treatment for safety and efficacy assessments. Subjects randomized to conservative care will additionally receive a clinical follow-up at 3 months to assess pain, change, or loss of function since their initial visit.

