9.2 Primary Endpoint

The primary efficacy endpoint of the study is improvement in the ODI at 6 and 12 months after treatment, and improvement in Visual Analogue Scale of Pain Intensity (VASPI) at 6 and 12 months after treatment.

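### Durability at 24 and 36 months is judged against the 12-month result, with no explicit allograft-versus-saline contrast, so it cannot show that an allograft effect lasts

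*Protocol*

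**What the plan says.** **Endpoint.** The Primary part of the Endpoints row in the protocol synopsis includes "Durability of Oswestry Disability Index (ODI) at 24 and 36 months after initial inclusion compared with 12 month improvement", with a parallel entry for VASPI. No test, margin or threshold is attached to either.

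**Extension population.** The Sample size and randomization row says "The original randomized population will be pooled and reconsented for an optional follow up for 24 and 36 months".

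**Comparator.** Protocol Section 3 describes the 24- and 36-month questionnaires as data "which will be analyzed and compared to the original 12-month data". For patients given allograft at 24 months it adds: "This data will be compared to the first 12 months of data in the placebo group". These are the only comparisons stated for the extension.

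**Status.** The protocol body disagrees with the synopsis. Section 6 says "Optional long term follow up at 24 and 36 months for all randomized subjects will allow for additional secondary endpoints to analyze pain". Section 9.2 says "The primary efficacy endpoint of the study is improvement in the ODI at 6 and 12 months after treatment" and treats VASPI in the same way; Section 7.2.1 also names only 6 and 12 months. The synopsis itself repeats 24- and 36-month ODI and VASPI improvement under Secondary.

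**SAP.** Sections 3.2.1 and 9.1 set ODI and VASPI at 12 months as co-primary and make trial success depend on both. Section 5.2 places the final analyses after the last 12-month visit. Durability is not mentioned. The SAP's preface lists a protocol issued in May 2018; the protocol under review is Rev 6 of December 2019.

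**Re-injection.** Under Protocol Section 7.1.7, all randomised patients who again meet the entry criteria may receive allograft at 24 months.

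**The concern.** Durability of a treatment effect is a statement about a difference between arms: allograft did better than saline at Month 12, and still does later. The comparison described here is a different one, a later score against the 12-month result. It asks whether scores held steady after Month 12.

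The two can part in either direction. If allograft has no effect and chronic back pain is simply stable in the second year, the comparison looks favourable. If allograft works at Month 12 and the saline arm then catches up while the allograft arm stays flat, the comparison again looks favourable although the effect has gone.

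The comparison of patients injected at 24 months with the placebo group's first year does not fill the gap. It sets re-selected patients, a later period and a second procedure against an earlier period in one arm, so it is neither concurrent nor randomised.

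What is at stake is a claim in the study report that the benefit lasts two or three years. It would rest on data that cannot separate a lasting effect from a stable course.

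**Working it through.** **The plan's own figure.** There is none for durability. The check borrows the ODI planning values of Protocol Section 13.3: SD 15.5, a minimum important difference of 6 points and a clinically relevant difference of 9. Two values derived from them there do reproduce: P(x<y) = Φ(−9/(15.5·√2)) = 0.341, and measurement error 15.5·√(1−0.75) = 7.75.

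**Step 1: why treatment arm drops out.** Write a patient's score at Month 12 as B + τ·A, where A = 1 for allograft and 0 otherwise, and at Month 24 as B + τ·A + δ. The later-minus-earlier difference is δ. The effect τ cancels, so τ = 0 and a large constant τ give the same result. This holds whether the arms are pooled or the allograft arm is taken alone.

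**Step 2: illustration with no average change after Month 12.** The success rules below are assumptions; the documents contain none. The SD of the within-patient change is 15.5·√(2(1−ρ)) and se = SD/√n. The 12-to-24-month correlation ρ is not given, so 0.5, 0.75 and 0.91 were tried (the last two are the plan's reliability range), with n from 40 to 220. The chance of meeting one comparison, whatever τ is:

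- No significant worsening, two-sided 0.05: Φ(1.96) = 97.5% at any n or SD.
- Observed mean not worse: 50%.
- Confidence limit excludes a 9-point loss: Φ(9/se − 1.96) = 96% to 100%. The low end is n = 40, ρ = 0.5: se = 15.5/√40 = 2.45.
- Confidence limit excludes a 6-point loss: Φ(6/se − 1.96) = 69% to 100%.

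Under the first rule, requiring ODI and VASPI together at one visit gives about 95–96%, and all four comparisons about 91–93% (assumed correlation 0 to 0.7 between the scores and 0.5 between the visits). A randomised between-arm test at two-sided 0.05 would favour a null allograft about 2.5% of the time.

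**Step 3: sensitivity to drift.** Keep the first rule, set n = 220 and let all arms worsen by 2 points: Φ(1.96 − 2/se) = 52% (ρ = 0.5), 23% (0.75) or 0.5% (0.91). With a further 3-point improvement it is about 100%. The result follows the average course of the patients, not the treatment.

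**Step 4: what a randomised contrast would cost in precision.** Half-width = 1.96·15.5·√(1/nA + 1/nS), taking 15.5 as the SD of change from baseline and assuming equal participation in each arm, since participation is not given:

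- 50% (70 allograft, 20 saline): 30.38·√(0.01429 + 0.05) = 7.7 points.
- 75% (105 allograft, 30 saline): 30.38·√(0.00952 + 0.03333) = 6.3 points.

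**Step 5: is the contrast feasible?** Section 7.1.7 and footnote f of Appendix A have the Month-24 questionnaires completed at the start of the visit, before the work-up for any injection. Pre-injection scores by randomised arm are therefore already collected. Saline is the cleaner comparator because conservative-care patients may cross over from Month 3 (Section 7.1.4).

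**The case against.** **Durability cannot decide the trial.** This stands. The protocol body calls these endpoints secondary, and SAP Section 9.1 ties success to the 12-month between-group tests alone. A reader of the synopsis might infer that a primary claim could be won on durability; the SAP rules that out. What remains is a conflict of status and an undefined analysis.

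**The 97.5% is not a property of the plan.** This also stands. It is 1 − 0.025 under an assumed rule with stable scores. A reader might infer that the endpoint is met almost always under no effect, or that pooling causes this. Neither is supported: the rate moves with rule and drift (Steps 2 and 3), and it is the same in one arm alone.

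**Pooled may not be an analysis rule.** Fair. The word sits beside reconsent in the sample-size row, not under Endpoints or Statistical Analysis. A reader might also infer that other arms could hide a real allograft loss. That needs a pooled analysis the documents do not state and, for substantial masking, improvement in the other arms after Month 12 that no section suggests.

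**A between-group test may already apply.** Protocol Section 13.2.2 compares pre-post differences between groups for the primary criteria. If durability is primary, this could be read to cover it. But that section names no visit, the synopsis null hypothesis is at 12 months, and the durability entries name the 12-month result as comparator. The contrast is at best implied.

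**Durability presupposes a 12-month effect.** If that is shown, stable scores in the allograft arm are useful description. They become evidence of a lasting effect only on the further assumption that saline patients would not have improved meanwhile.

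**Conclusion.** The point holds as one of definition and reconciliation. The synopsis makes 24- and 36-month durability primary and benchmarks it on Month 12. It gives no success rule and specifies no explicit concurrent allograft-versus-saline contrast; the protocol body and the SAP disagree with its status. As described, the comparison cannot distinguish a lasting allograft effect from a stable course. That conclusion rests on the structure of the comparison and needs no assumed number.

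The size is conditional: 97.5% per comparison if durable means no significant worsening and scores are truly stable, and anything from near 0% to 100% under other rules or drift. The 12-month success criterion is unaffected. Month 36 is weaker still, because those scores may follow a new injection at Month 24.

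**What to change.** 1. Give durability one status across the synopsis, the protocol body and the SAP, and bring the SAP into line with the current protocol.
2. Analyse it by original randomised arm: the allograft-minus-saline difference in change from baseline in ODI and VASPI at Month 24, with a 95% CI, from scores taken before any Month-24 injection. Show the same difference at Month 12 in the same patients beside it.
3. Report the within-arm Month 12-to-24 change with its CI. For ODI, read it against the plan's own 6- and 9-point figures, not by p > 0.05.
4. Say whether pooled refers to reconsent or to analysis. Label any pooled summary as descriptive.
5. Label Month-36 results that may follow a new injection as descriptive, and show them separately by whether the patient was re-injected.

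**Cost.** Wording in the protocol and SAP and a small set of tables; no new data or patients. There are three downsides to state openly. Precision is limited (half-widths of about 7.7 and 6.3 ODI points, from Step 4). Patients are unblinded on signing the extension consent (Protocol Section 6.3), which precedes the Month-24 questionnaires, so those self-reports are unblinded. The extension sample is self-selected, so randomisation protects the contrast only in part.
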